7.0 Statistical Analysis Plan

7.1 Definitions

- 7.1.1 Escalation: Changing to a broader spectrum antibiotic (higher number category in Tables 5 and 6), addition of one or more antibiotics, or conversion of oral (PO) to intravenous (IV) route.
- 7.1.2 De-escalation: Changing to a narrower spectrum antibiotic (lower number category in Tables 5 and 6) cessation of one or more antibiotics, or changing from an IV to PO route of appropriate drug (i.e. PO ciprofloxacin or levofloxacin).

Table 5. Gram negative agents

Category	Spectrum	Antibiotics
1	Narrowest	Ampicillin, cefazolin
2	Narrow	Amoxicillin/clavulanic acid, ampicillin/sulbactam, 2 nd -generation cephalosporins, 3 rd generation cephalosporins (except ceftazidime), PO fluoroquinolones (ciprofloxacin, moxifloxacin, levofloxacin), metronidazole, tetracyclines, trimethoprim-sulfamethoxazole,
3	Medium	Aminoglycosides (amikacin, gentamicin, tobramycin), ceftaroline, ceftazidime, IV fluoroquinolones (ciprofloxacin, moxifloxacin, levofloxacin), fosfomycin
4	Medium broad	Anti-Pseudomonal penicillin/penicillinase combinations, aztreonam, cefepime, ertapenem
5	Broadest	Anti-Pseudomonal carbapenems, ceftazidime/avibactam, ceftolozane/tazobactam, polymyxins, tigecycline

Table 6. Gram positive agents

Category	Spectrum	Antibiotics
1	Narrow	Ampicillin, cefazolin, clindamycin, erythromycin, nafcillin, oxacillin, trimethoprim-sulfamethoxazole, tetracycline, azithromycin
2	Medium	Dalbavancin, IV vancomycin
3	Broad	Ceftaroline, daptomycin, IV/PO linezolid, oritavancin, quinupristin/dalfopristin, IV/PO tedizolid

7.2 Outcome Measures

7.2.1 Primary Outcome Measures

- Mean time until first modification of antibiotic therapy (in hours) within 72 hours post randomization

7.2.2 Secondary Outcome Measures

- In-hospital mortality within 30 days of randomization
- Length of stay in the hospital after randomization, up to 30 days, for those patients alive at 30 days. Length of stay will be date of discharge minus date of randomization.
- < 72 hours or ≥72 hours in the ICU after randomization.
- Mean time to antibiotic escalation in those who have antibiotic escalation within 72 hours from randomization. This will be further broken down by whether the escalation was in gram positive coverage, gram negative coverage, or both.
- Mean time to antibiotic de-escalation in those who have antibiotic de-escalation within 72 hours from randomization. This will be further broken down by whether the de-escalation was in gram positive coverage, gram negative coverage, or both.
- Hospital-onset *Clostridium difficile* within 30 days, as defined by the National Healthcare Safety Network (NHSN). This will be normalized to patient-days.²²
- Acquisition of new hospital-acquired infections (HAIs) and/or multidrug resistant organisms (MDROs) within 30 days during index hospitalization identified on routine clinical or surveillance samples. This will be normalized to patient-days. Cultures that will be tracked include the following, from any specimen source, unless otherwise indicated:
 - Methicillin-resistant *Staphylococcus aureus*
 - Vancomycin-resistant *Enterococcus*
 - 3rd generation cephalosporin non-susceptible *Enterobacteriaceae*
 - Carbapenem-resistant *Enterobacteriaceae*, as defined by the CDC: resistant to imipenem, meropenem, doripenem, or ertapenem OR documentation that the isolate possesses a carbapenemase²³
 - Multidrug-resistant *Pseudomonas aeruginosa* (resistant to aminoglycosides, cephalosporins, fluoroquinolones, and carbapenems)²⁴
 - Carbapenem-resistant *Acinetobacter*
 - *Candida* species (isolated from blood cultures only)

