Secondary Objectives	To evaluate the impact of rapid identification and AST on antimicrobial utilization and clinical outcomes. 
 • 30-day mortality • Length of stay in the hospital • Days in the ICU • Duration of broad-spectrum gram-negative coverage in the first 72 hours following randomization • Mean time to antibiotic escalation • Mean time to antibiotic de-escalation • Hospital-onset Clostridium difficile • Acquisition of new hospital-acquired infections (HAIs) and/or multidrug resistant organisms (MDROs)
Study Population	All patients with blood culture bottles growing gram-negative bacilli (GNB) detected on Gram staining will be eligible
Number of subjects	500 subjects
Number of sites	2 sites
Clinical Samples	Clinically collected blood cultures with growth of GNB detected by Gram stain
Start of Enrollment:	October 2017
End of Enrollment:	October 2018

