5.5.3 Antibiotic spectrum and antibiotic intensity score

The antibiotic intensity score will be determined as follows: Each antibiotic is assigned an antibiotic spectrum rank from 1-5 (see Table 4). The antibiotic rank will be multiplied by the duration each antibiotic is received (in hours) within the first 72 hours following randomization. For patients receiving multiple antibiotics, the total antibiotic intensity

score will be the summation of the rank x duration product for each antibiotic. If a single dose of antibiotic is administered, duration will be considered 1 hour. For all antibiotics given for more than one dose, the duration will be the time of administration of the last dose minus the time of administration of the first dose (or time of randomization, if subject was receiving antibiotic at randomization) plus one hour. Patients who die before 72 hours will be assigned the highest intensity score among patients in the study who were alive at 72 hours.

Table 4. Antibiotic spectrum rank, categorized by clinical use and spectrum

Intensity score	Rank	Antibiotics
1	Narrowest	Amoxicillin, ampicillin, first-generation cephalosporins, clindamycin, dalbavancin, daptomycin, dicloxacillin, linezolid, macrolides, metronidazole, nafcillin, oritavancin, oxacillin, penicillin, quinupristin/dalfopristin, rifampin, tedizolid, vancomycin
2	Medium narrow	Amoxicillin/clavulanic acid, ampicillin/sulbactam, 2 nd -generation cephalosporins, 3 rd generation cephalosporins (except ceftazidime), PO fluoroquinolones (ciprofloxacin, moxifloxacin, levofloxacin), tetracyclines, trimethoprim-sulfamethoxazole,
3	Medium	Aminoglycosides (amikacin, gentamicin, tobramycin), ceftaroline, ceftazidime, IV fluoroquinolones (ciprofloxacin, moxifloxacin, levofloxacin), fosfomycin
4	Medium broad	Anti-Pseudomonal penicillin/penicillinase combinations, aztreonam, cefepime, ertapenem
5	Broadest	Anti-Pseudomonal carbapenems, ceftazidime/avibactam, ceftolozane/tazobactam, polymyxins, tigecycline

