7.2.3 Exploratory Analyses

- Standardized costs, obtained from the UHC/Vizient database
- The primary endpoint will be analyzed comparing patients who are:
 - in the ICU at baseline versus not in the ICU at baseline
 - neutropenic at baseline versus not neutropenic at baseline
- The primary endpoint will be analyzed excluding antibiotic modifications made within the first hour after randomization, as these changes may be in response to Gram stain result rather than AXDX result
- 30-day readmission to the index hospital
- The proportion of discrepancies (as detailed in 6.0) between rapid testing and standard of care testing among subjects who receive rapid testing (arm 2)
- Antibiotic intensity score (as detailed in 5.5.3) in the first 72 hours post randomization

- Desirability of outcome response and response adjusted for antibiotic risk within 72 hours (DOOR-RADAR) score (see Table 7 below)

Table 7. Desirability of outcome response (DOOR) ranking table.

DOOR Rank	30-day mortality	In ICU at 72h post-randomization	HO-CDI*	New resistant or hospital-acquired organism**
1	Alive	No	No	No
2	Alive	No	Yes	No
3	Alive	No	No	Yes
4	Alive	No	Yes	Yes
5	Alive	Yes	No	No
6	Alive	Yes	Yes	No
7	Alive	Yes	No	Yes
8	Alive	Yes	Yes	Yes
9	Dead	--	--	--

*HO-CDI, Hospital onset *C. difficile* infection

**Newly acquired within 30 days post-randomization, from clinically collected or surveillance cultures

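### Read literally, the 72-hour ICU outcome groups early deaths with little or no ICU care, and mortality is in-hospital in some sections and 30-day in others

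*Combined protocol and SAP*

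**What the plan says.** **ICU.** Section 7.2.2 splits patients by "< 72 hours or ≥72 hours in the ICU after randomization". Neither that section nor 7.4.2 says how a death is classified. The synopsis names the outcome "Days in the ICU", and the DOOR ranking in Table 7 (7.2.3) uses "In ICU at 72h post-randomization". For a different outcome, the antibiotic intensity score, 5.5.3 does have an early-death rule: "Patients who die before 72 hours will be assigned the highest intensity score among patients in the study who were alive at 72 hours".

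**Mortality.** Section 7.2.2 has "In-hospital mortality within 30 days of randomization". Section 5.5.4 follows patients to discharge, or to day 30 if they are still in hospital. The synopsis and Table 7 say "30-day mortality", and Appendix I schedules collection of vital status to day 30 at close of study.

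**Length of stay.** Section 7.2.2 specifies "Length of stay in the hospital after randomization, up to 30 days, for those patients alive at 30 days". That population cannot be formed without day-30 status for patients already discharged.

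**Data source.** Sections 5.5 and 5.5.4 name the electronic medical record (EMR). There is no consent (5.1) and no direct interaction with patients (8.1). Readmission is tracked as "30-day readmission to the index hospital".

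**The concern.** A patient who dies before 72 hours cannot accumulate 72 ICU hours. The split therefore places an early ICU death in the shorter-stay group, beside patients who were never in the ICU. If rapid testing prevented some early deaths and those patients then had long ICU stays, the ICU outcome would count that benefit as harm.

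The mortality problem is inconsistency. Two competent analysts could follow this plan and report different mortality and DOOR results. An in-hospital definition also ties the window for counting deaths to discharge timing, so it can shrink, leave unchanged or enlarge a 30-day difference. These are the clinical outcomes that will be read beside the primary result.

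**Working it through.** **Inputs.** 200 evaluable patients per arm (7.3). The plan's power figure is for the primary outcome only: 9 hours, SD 32, two-sided alpha 0.05. It reproduces at 80.3% against the stated 80% and does not depend on anything below. The documents give no ICU, death or discharge rates, so every rate below is an assumption.

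**1. Placement of early deaths.** Let 25% of 72-hour survivors in both arms have >=72 h in the ICU, with early deaths of 2% in one arm and 5% in the other. The difference in the >=72 h share (second arm minus first) is:
- Deaths counted as <72 h (literal): 0.25 × 0.95 − 0.25 × 0.98 = 23.75% − 24.50% = −0.75 points. The arm with more deaths looks better.
- Deaths counted as unfavourable: 28.75% − 26.50% = +2.25 points.
- Deaths excluded: 0.

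With 15% or 35% in place of 25%, the literal result is −0.45 or −1.05 points and the unfavourable one +2.55 or +1.95. The gap between the two rules always equals the difference in early deaths (3 points here), and is zero when early deaths are equal.

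**2. Literal outcome when deaths are prevented.** Suppose 2-6% of the standard arm (4-12 of 200) die in the ICU before 72 h and rapid testing prevents half, so 1-3% are saved.
- All those saved stay >=72 h: the outcome worsens by 1-3 points.
- All those saved leave the ICU before 72 h: it changes by 0.

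SE of the difference = 100 × sqrt(2p(1−p)/200), where p is the share with >=72 h: 3.57 points at p = 0.15, 4.33 at 0.25, 4.77 at 0.35. The non-zero shifts run from 1/4.77 = 0.21 to 3/3.57 = 0.84 SE.

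**3. Ordered outcome in the same scenarios.** Order the categories as dead by 72 h, alive with >=72 h, alive with <72 h. The standard arm is (d, 0.25, 0.75 − d). The measure is P(rapid better) + 0.5 × P(tie).
- Those saved stay >=72 h: 0.5014, 0.5029, 0.5047 for d = 0.02, 0.04, 0.06.
- Those saved leave before 72 h: 0.5063, 0.5125, 0.5188.

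Check of the last value: standard (0.06, 0.25, 0.69), rapid (0.03, 0.25, 0.72). Better = 0.25 × 0.06 + 0.72 × 0.31 = 0.2382. Tie = 0.0018 + 0.0625 + 0.4968 = 0.5611. Sum = 0.2382 + 0.2806 = 0.5188.

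The tie-corrected SE is about 0.022-0.023, so the movement is about 0.06-0.8 SE, in the right direction.

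**4. ICU wording.** The three measures are not interchangeable. A patient who enters the ICU at hour 60 and leaves at hour 80 has 20 ICU hours, so is in the <72 h group of 7.2.2, but counts as in the ICU at 72 h in Table 7.

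**5. Mortality definitions.** Take a patient discharged on day 10 who dies on day 20.

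| Place | Classification |
|---|---|
| 7.2.2 mortality | Not an event |
| Synopsis mortality | Event |
| Table 7 (DOOR) | Dead, rank 9 |
| 7.2.2 length of stay | Excluded |
| 5.5.4 follow-up | Ends on day 10, death not sought |

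If 30-day mortality is 8-15% and 10-40% of those deaths follow discharge, the definitions differ by 200 × 0.08 × 0.10 = 1.6 to 200 × 0.15 × 0.40 = 12 deaths per arm.

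The effect on the arm difference has no fixed sign. With true mortality of 12% vs 8%, the in-hospital difference is 4 − (post-discharge deaths, standard − rapid, in points):
- 10-30% of deaths after discharge in both arms: 3.6 to 2.8 points
- 2 points after discharge in each arm: 4
- 1 vs 2 points: 5
- 4 vs 0 points: 0

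These show direction only and are not forecasts.

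**The case against.** The strongest reply is that the plan can be run as written. The literal ICU split classifies every patient. Mortality is a separate secondary outcome, so the ICU result is not read alone, and DOOR already ranks death below ICU status. The 7.2.2 mortality definition agrees with 5.5.4, and the synopsis is only a list of objectives. The effects are small, and a day-30 definition brings unknown vital status that an in-hospital one avoids.

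Much of this stands, and it rules out several stronger readings that a reader might infer:
- **That the ICU outcome cannot be computed.** It can. The fault is where it puts early deaths.
- **That Table 7 supplies an early-death rule.** Rank 9 is any death by day 30. Only 5.5.3 addresses early death, and for another outcome.
- **That no source exists for deaths.** The EMR is the named source. The open question is how complete it is after discharge.
- **That survivors-only length of stay is an error.** It is explicit and prespecified. It does condition on a post-randomization event, but adding an analysis that includes deaths is a preference.

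Two things do not yield. DOOR is exploratory and uses ICU status at a time point, so it does not repair the secondary ICU outcome. And the synopsis is not the only conflict: Table 7, Appendix I and the length-of-stay population in 7.2.2 itself all need day-30 status.

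**Conclusion.** The point holds for two secondary outcomes and for the DOOR and length-of-stay definitions that share their inputs. The literal ICU split can favour the arm with more early deaths, and mortality has two definitions with follow-up that fits only one.

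The likely size is modest. If half of 2-6% early ICU deaths are prevented, the ICU outcome worsens by 0-3 points, at most about 0.8 SE, and by nothing if early deaths are equal by arm. The true early-death rate may be lower than assumed, because patients on comfort care at randomization are unevaluable (7.4.1). The ordered outcome corrects the direction but adds little power.

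A reader might infer that the trial's main result is at risk. It is not: the primary outcome and sample size do not use these definitions. Severity is minor to moderate.

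**What to change.** **ICU.** Analyse an ordered outcome: dead by 72 h (worst), alive with >=72 h in the ICU, alive with <72 h including none. Align the synopsis with 7.2.2, and state why Table 7 differs if its time-point component is kept. The cost is SAP wording.

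**Mortality.** Use one definition in the synopsis, 7.2.2, 5.5.4, Table 7 and the length-of-stay population: all-cause death by day 30, from the Appendix I item, with in-hospital mortality as supportive. Report unknown day-30 status by arm. State one rule for it (for example, count as alive) and one sensitivity analysis (count as dead, DOOR rank 9), and apply both to mortality and DOOR.

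**Fallback.** If the EMR cannot establish deaths after discharge, label the outcome in-hospital mortality everywhere, including DOOR, and reword the length-of-stay population to match. This is a wording edit.

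**Cost of the day-30 option.** Some discharged patients will have unknown status. If 80-90% are discharged alive and 5-15% of these are unknown (assumed), that is 200 × 0.80 × 0.05 = 8 to 200 × 0.90 × 0.15 = 27 per arm. Equal numbers by arm leave the difference unchanged under either rule. A 5-point imbalance in the unknown share moves the count-as-dead result by 0.80 × 5 = 4.0 to 0.90 × 5 = 4.5 points. The completeness of the EMR should therefore be checked before choosing.

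**Optional.** A rank-based length-of-stay analysis with death as worst could be added as a remark, but it is not required.

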3.2 Secondary Objectives

Secondary objectives will be to evaluate the impact of rapid identification and AST on antibiotic utilization and clinical outcomes.

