5.5.4 Outcomes

Final outcomes for each enrolled patient will be gathered retrospectively from the EMR. Patients will be followed for the duration of their hospitalization, or up to 30 days if they remain hospitalized.

Inpatient hospitalization cost data will be obtained from Vizient/University Health Consortium (UHC).

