7.4.2 Analysis of secondary and exploratory outcomes

We will compare all secondary and exploratory outcomes between the rapid testing and standard testing arms. Where interest lies in mean differences, we will follow the same approach as for the primary outcome. The DOORs will be compared between arms to estimate the probability (with 95% CI) that a randomly selected participant will have a better DOOR outcome if assigned to rapid testing. We will determine the proportion of very major errors and very major or major errors among patients who receive rapid testing.

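### The synopsis objective on ICU days has no matching outcome: Section 7.2.2 specifies only a split at 72 hours, so the planned analysis will not estimate a difference in ICU days

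*Combined protocol and SAP*

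**What the plan says.** Three places in the combined protocol and SAP describe an ICU measure, and each is different.

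- The Protocol Synopsis, under secondary objectives, lists "Days in the ICU". Section 3.2 does not itemise: "Secondary objectives will be to evaluate the impact of rapid identification and AST on antibiotic utilization and clinical outcomes". The synopsis is therefore the only itemised list of secondary objectives.
- Section 7.2.2 gives the secondary outcome as "< 72 hours or ≥72 hours in the ICU after randomization".
- Section 7.2.3, Table 7, uses "In ICU at 72h post-randomization" as a yes/no component of the exploratory DOOR ranking.

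Hospital stay, in the same Section 7.2.2, remains a duration. It has a formula, "Length of stay will be date of discharge minus date of randomization", a 30-day limit, and a restriction to patients alive at 30 days.

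For analysis, Section 7.4.2 says "Where interest lies in mean differences, we will follow the same approach as for the primary outcome". It names no method for a two-category ICU outcome. On data, Section 5.5.4 says "Final outcomes for each enrolled patient will be gathered retrospectively from the EMR" and "Patients will be followed for the duration of their hospitalization, or up to 30 days if they remain hospitalized".

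**The concern.** The objective is a duration and the outcome is one cut through it. A patient who leaves the ICU on day 4 and one still there on day 30 fall in the same category, as do a patient with no ICU time and one with 71 hours. A benefit or harm that acts within either category does not register, and the result cannot be expressed in days beside hospital stay and cost.

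The split is also loosely defined. Section 7.2.2 does not say whether it means cumulative ICU hours or one continuous stay, and it has no rule for early deaths. Read literally, a patient who dies in the ICU at hour 20 is classed as under 72 hours, which looks like the favourable category. With three ICU measures in the documents and no stated link between them, there is room to choose the emphasis after the data are seen.

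**Working it through.** **1. What the plan's own figures cover.** The only power statement concerns the primary outcome: 200 evaluable per arm, difference 9 h, SD 32 h, two-sided alpha 0.05 (Section 7.3). The standard error is 32 × √(2/200) = 3.2 h, 9/3.2 = 2.81, and 2.81 − 1.96 = 0.85, which gives 80.3% power against the stated 80%. It reproduces, but says nothing about the ICU outcome. The documents give no ICU rate, mean stay or SD, so every ICU figure below rests on assumptions.

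**2. What the split cannot see.** Assume that 70% of patients have no ICU time, 15% have 1.5 days, and 15% stay beyond 72 h. Mean ICU days = 0.15 × 1.5 + 0.15 × L, where L is the length of the long stays.

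| L (days) | Share ≥72 h | Mean ICU days |
|---|---|---|
| 4 | 15% | 0.225 + 0.600 = 0.83 |
| 6 | 15% | 0.225 + 0.900 = 1.13 |
| 10 | 15% | 0.225 + 1.500 = 1.73 |

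The mean doubles from the first row to the last while the split reads 15% throughout.

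**3. What the split can see.** With 200 per arm and 80% power, if the share at or above 72 h is 10%, 20%, 30% or 40% in one arm (assumed), the detectable absolute reduction is about 7, 10, 12 or 13 points. Check at 20% versus 10%: SE = √((0.20 × 0.80 + 0.10 × 0.90)/200) = 0.0354, 0.10/0.0354 = 2.83, and 2.83 − 1.96 = 0.87, so power is about 81%.

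**4. Power of the split against mean days.** Simulation with 200 per arm. A stated share has ICU time and the rest have zero. Stays are lognormal with CV 1.2, capped at 30 days. The split is tested by chi-square and days by the unequal-variance t-test.

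| Assumed share with ICU time | Assumed mean stay | 30% cut: split vs days | 50% cut: split vs days |
|---|---|---|---|
| 35% | 4.5 d | 29% vs 32% | 80% vs 80% |
| 50% | 4.5 d | 45% vs 45% | 95% vs 95% |
| 35% | 7 d | 24% vs 32% | 75% vs 83% |
| 50% | 7 d | 34% vs 46% | 92% vs 96% |

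Repeat runs moved these figures by a point or two. At a mean of 4.5 days there is no gain beyond simulation error. At 7 days it is roughly 4 to 12 points. Neither measure reaches 50% power for a 30% cut.

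**5. A benefit confined to long stays.** In the same settings, halve only the ICU time beyond day 3. Nobody crosses 72 h, so the split rejects at about 5%, which is chance. Mean days has about 22% to 58% power for a true difference of 0.4 to 1.0 day.

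**6. Agreement with Table 7.** A patient who enters the ICU at hour 70 for one day is in the ICU at 72 h (Table 7: yes) but has 24 ICU hours (Section 7.2.2: under 72 h). Conversely, ICU time over hours 0 to 70 and 80 to 100 gives 70 + 20 = 90 cumulative hours, but the patient is out of the ICU at 72 h. For a patient continuously in the ICU from randomization, the two measures agree.

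**The case against.** The strongest reply is that a synopsis is shorthand and Section 7.2.2 makes it operational. It does so elsewhere: 30-day mortality in the synopsis becomes in-hospital mortality within 30 days. The 72-hour mark matches the window of the primary outcome and of the antibiotic data. The outcome is secondary, no power is claimed for it, and the mismatch could be removed by editing the synopsis. This has force as to seriousness. It does not remove the mismatch, because no other section itemises the secondary objectives and no reason is given for replacing a duration with a cut while hospital stay remains a duration.

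A reader might infer that the trial will be unable to say anything about ICU time. The documents do not support that. A difference between arms in the share at or above 72 h would show that ICU time changed, though not by how many days.

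A reader might also infer from Appendix I, which has no row for ICU entry or exit, that the dates will not be collected. That does not follow. The 72-hour split and the Table 7 ICU status have no row there either, yet both need ICU times, and Section 5.5.4 takes outcomes from the medical record over the hospitalization, up to 30 days.

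The difference between the split and Table 7 is minor in itself. Two endpoints need not coincide, status at 72 h is a legitimate component of an exploratory ranking, and disagreement requires ICU entry or re-entry after randomization, whose frequency the documents do not give.

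Finally, moving to ICU days without a rule for deaths would replace one under-specified outcome with another, since death in the ICU shortens ICU days and would look like benefit. That is correct, and the fix has to deal with it.

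**Conclusion.** The point holds as a gap in pre-specification. The synopsis objective has no matching outcome, the planned analysis will not estimate a difference in ICU days, and changes that stay on one side of 72 h will be missed. The split remains a usable but coarse measure.

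The case does not rest on power. The gain of about 0 to 12 points depends wholly on assumed ICU rates and stays, and vanishes at the shorter ones. A larger gain appears only if the effect is confined to stays already past day 3, which is also an assumption. What is lost under any assumption is an estimate in days that answers the stated objective. For a secondary outcome with an inexpensive correction, this should be changed, but it does not threaten the trial's primary conclusion.

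**What to change.** In Section 7.2.2:

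- Add ICU days from randomization to day 30 as the outcome that answers the synopsis objective, with patients never in the ICU counted as zero.
- Handle deaths by the rule already used for hospital stay (patients alive at 30 days), and report deaths by arm alongside, because a comparison restricted to survivors should not be read alone.
- Analyse the difference in means with a 95% CI by the approach in Section 7.4.2.
- Keep the 72-hour split as supportive. State whether it means cumulative ICU hours, how deaths before 72 h are classed, and which effect measure and test will be used, since Section 7.4.2 names none for a two-category outcome.
- Derive ICU days, the split and the Table 7 ICU status from the same ICU entry and exit times in the medical record. Listing those times in Appendix I would make the source explicit.

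The cost is one extra secondary analysis, some SAP wording, and abstraction of entry and exit times for each ICU stay from records already reviewed for outcomes.
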